19 CLINICAL TRIAL AGREEMENT

Before the study commences, a Clinical Trial Agreement be will signed in which financial aspects of the study (including financial disclosure) as well as responsibilities and obligations are described. This will take the form of:

- A contract between [REDACTED] and the Investigator/healthcare organisation.

20 COMPENSATION, INDEMNITY AND INSURANCE

20.1 Compensation

Appropriate treatment and/or compensation will only be provided and/or paid to the patient by the Sponsor to the extent that a patient suffers injury or death directly attributable to participation in the study without:

- Fault on the part of the investigator or the CRO or its employees or agents.
- The investigator or the CRO failing to comply with the protocol.
- The investigator or the CRO failing to notify the Sponsor of the claim or denying the Sponsor full conduct of the claim.

In any event, such compensation and treatment shall only be provided by the Sponsor to the extent required by the applicable law.

20.2 Indemnity

RB will provide appropriate indemnity for the Investigator and staff who conduct part or all of this study, upon request. The request must be received before the first patient is recruited.

20.3 Insurance

If required, and in accordance with applicable regulatory and legal requirements, RB will take out appropriate insurance policies on behalf of the Investigator and staff who conduct part or all of this study, and/or on behalf of the patients participating in the study.

21 REPORTING, PUBLICATION AND PRESENTATION

A clinical study report will be prepared according to ICH E3 (Structure and Content of Clinical Study Reports) as part of RB's commitment to Good Clinical Practice. The report will be a record of the total study conduct and findings, and will be subject to approval by the Co-ordinating Investigator who will sign the final report.

The study data will be owned by RB. RB retains the right to publish the data independently of the Investigator. RB agrees that before it publishes the results, it will provide the Investigator with at least 30 days for full review prior to submission of the manuscript to the publisher. The Investigator must submit any proposed manuscript to RB for approval prior to submission for publication.

Any publication must state that it is a part of a multicentre study. Where it would be impractical to send the manuscript to every Investigator in a multicentre study, a copy will be sent to the Co-ordinating Investigator. In such a study, RB may wish to publish the results of the study and this may be done without all participants having the opportunity to review the manuscript.

23 APPENDICES

There are no appendices.

 Reckitt Benckiser <small>HEALTH • HYGIENE • HOME</small>	Non Substantial Amendment Form SOP D0365585, Version 4.0, Page 1 of 5
---	--

Reckitt Benckiser

PROTOCOL NON SUBSTANTIAL AMENDMENT NUMBER [1]

PRINCIPAL INVESTIGATOR:

[REDACTED]
[REDACTED]
[REDACTED]
[REDACTED]
[REDACTED]

China

DETAILS OF PROTOCOL AMENDMENT:

1. Section(s) to be Changed:

Section 5.1, Table 5.1 – Reckitt Benckiser Details, page 18

From:

Name	Position	Address and Contact Number
[REDACTED]	Clinical Project Manager	Reckitt Benckiser Healthcare (UK) Ltd, [name]. UK. [REDACTED]
[REDACTED]	Global Medical Director	Reckitt Benckiser Healthcare (UK) Ltd, [name]. UK. [REDACTED]
[REDACTED]	Senior Statistician	Reckitt Benckiser Healthcare (UK) Ltd, [name]. UK. [REDACTED]

 Reckitt Benckiser <small>HEALTH • HYGIENE • HOME</small>	Non Substantial Amendment Form SOP D0365585, Version 4.0, Page 2 of 5
---	--

Revised Paragraphs:

Name	Position	Address and Contact Number
[REDACTED]	Clinical Project Manager	Reckitt Benckiser Healthcare (UK) Ltd, [name], UK, Telephone No: [REDACTED]
[REDACTED]	Reckitt Benckiser Medical Officer	Reckitt Benckiser Healthcare (UK) Ltd, [name]. [REDACTED]
[REDACTED]	Statistical Manager	Reckitt Benckiser Healthcare (UK) Ltd, [name]. Tel [REDACTED]

Reason for Change:

Change of the person responsible at the Sponsor Company for medical cover of the study.

2. Section(s) to be Changed:

pH Monitoring table footnote in Section 3.10, page 8 and Section 11.2, page 34

From:

Revised Paragraphs:

Addition of the following words "The timings in this table are for guidance only. For full details see GA1202 pH Monitoring Guidelines" as a footnote to the pH monitoring table.

Reason for Change:

Clarification that the timings for pH monitoring procedures are only used for guidance. The pH monitoring guidelines provide full details of the methods.

 Reckitt Benckiser <small>HEALTH • HYGIENE • HOME</small>	Non Substantial Amendment Form SOP D0365585, Version 4.0, Page 3 of 5
---	--

3. Section(s) to be Changed:

Section 12.2, Identity of Non-Investigational Medicinal Products, page 45

From:

Compound Sodium Alginate Double Action Chewable Tablets will be manufactured to Good Manufacturing Practice (GMP) by Reckitt Benckiser Healthcare (UK) Limited, [name], UK (Product Licence 00063/0157).

1. INTRODUCTION

This document describes the rules and conventions to be used in the presentation and analysis of efficacy and safety data for Protocol GA1202. It describes the data to be summarized and analyzed, including specifics of the statistical analyses to be performed.

This statistical analysis plan (SAP) is based on protocol version 2, amendment 1, dated 4Jul2013.

2. STUDY OBJECTIVES

2.1. PRIMARY OBJECTIVE

The primary objective is to compare the time during the 4 hour post dosing period where the pH is below pH 4 for Compound Sodium Alginate Double Action Chewable Tablets versus matching placebo tablets.

2.2. SECONDARY OBJECTIVES

The following secondary endpoints will also be evaluated:

- Percentage of time during the 4 hour post dosing period with pH below pH 5
- Number of occasions during the 4 hour post dosing period when pH falls below pH 4
- Number of occasions during the 4 hour post dosing period when pH falls below pH 5
- Number of reflux episodes during the 4 hour post dosing period with pH below pH 4 for at least 5 minutes
- Percentage of time during the first hour post dosing with pH below pH 4
- Percentage of time during the first hour post dosing with pH below pH 5
- Number of occasions during the first hour post dosing when pH falls below pH 4
- Number of occasions during the first hour post dosing when pH falls below pH 5
- The longest reflux time during the 4 hour post dosing period (i.e. the longest period with pH below pH 4)
- The DeMeester scores during the 4 hour post dosing period.

3. STUDY DESIGN

3.1. GENERAL DESCRIPTION

This is a multi-centre, randomised, open-label, placebo-controlled, two-period crossover study. Forty - four (44) patients are planned to be enrolled in this study to ensure that thirty six (36) patients complete it. After signing a written informed consent, patients will undergo a screening period up to 10 days. Patients who satisfy the study entry requirements within 10 days of consent, will be randomised to receive either four Compound Sodium Alginate Double Action Chewable Tablets or four matching placebo tablets following placement of a pH electrode and a standardised refluxogenic meal.

Upon completion of the 4-hour post-dose pH monitoring period patients will be instructed to begin taking supplied Compound Sodium Alginate Double Action Chewable Tablets (two tablets four times daily) for 7 days. Patients will return after the 7 day period for repeat catheter insertion and pH monitoring, receiving the alternative randomised treatment.

3.2. SCHEDULE OF EVENTS

Schedule of assessments can be found in Section 3.10 of the protocol.

4. FINAL ANALYSIS

All final, planned analyses identified in this SAP will be performed by Quintiles Biostatistics following Reckitt Benckiser's Authorization of this SAP, Database Lock and Sponsor Authorization of Analysis Sets.

5. ANALYSIS SETS

Agreement and authorization of patients included/excluded from each analysis set will be conducted at data review meeting before database lock.

5.1. FULL ANALYSIS SET [FAS]

All patients enrolled (e.g. those assigned randomization number) in the study will be included in full analysis set (FAS).

Document: Reckitt Benckiser GA1202 Statistical Analysis Plan

Author: [REDACTED]

Version Number:

Final 5.1

Version Date:

[25Feb2014]

Template No: CS_TP_BS016 – Revision 3

Reference: CS_WI_BS005

Effective Date: 01May2012

Page 9 of 29

5.2. SAFETY POPULATION

All patients who are subjected to any invasive procedures and/or take at least one dose of study medication will be included in safety population.

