9.6.2 Invasive Procedures

Blood samples will be taken for haematology and clinical chemistry at Visit 1 and Visit 3. The total volume of blood samples will not exceed 30 ml.

An endoscopy will be performed at screening or results may be used if conducted prior to consent within 28 days of giving consent if the examination was conducted at the same hospital.

pH reflux monitoring for a period of 4.5 hours will take place on two occasions. This requires placement of the pH monitoring probe via one nostril, down the back of the throat, and into the esophagus as the patient swallows. Esophageal manometry is used to guide the accurate placement of the pH electrodes.

Further details on the study assessments are provided in Section 11.2.

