10 STUDY POPULATION

10.1 Inclusion Criteria

Only patients to whom all of the following conditions apply will be included:

1. Informed consent has been obtained.
2. Age: ≥ 18 years to ≤ 65 years.
3. Sex: male or female.
4. Primary diagnosis: meet the diagnostic criteria for GERD with a GERD history of frequent episodes of GERD-related symptoms during the last 2 months prior to study screening. The patient must also meet the following criteria:
 - a. The only or main symptom is heartburn (burning feeling back of breast bone) and/or acid reflux. Symptoms persists or have occurred repeatedly for more than 2 months;
 - b. As assessed by the Investigator at screening by questioning of the patient, the frequency of occurrence of heartburn is ≥ 3 days/week and the score of severity of heartburn in general is \geq Level 2 within 3 weeks before screening;

The severity of heartburn will be evaluated as follows:

Level 0	no heartburn
Level 1	heartburn is mild in severity and is not obvious
Level 2	heartburn is moderate, or it is obvious when it occurs, the patient experiences discomfort
Level 3	heartburn is severe and significant, seriously interferes with daily activities

The frequency of heartburn will be evaluated as number of days /week that heartburn is suffered (0, 1, 2, 3, 4, 5, 6 or 7 days).

5. Status: Patients will be patients at the clinic or members of the public who respond to an advertisement or via their doctor.
6. Patients who have not taken any antacids within 24 hours before randomisation (Visit 2) and be instructed not to take antacids, other than the Compound Sodium Alginate Double Action Chewable Tablets provided, throughout the remainder of the study.
7. Patients taking mucous membrane protection drugs or prokinetics may enter the study provided that these are discontinued for at least 5 days before screening and throughout the remainder of the study.
8. Systemic glucocorticosteroids or non-steroidal anti-inflammatory drugs (NSAIDs, except for low dose aspirin which can be given for cardioprotection) can only be taken for up to 3 consecutive days in the 28 days prior to screening.
9. Absence of relevant abnormalities in the physical examination, endoscopy, ECG and laboratory safety results.
10. Patients who are willing to consume the entire standard refluxogenic test meal.
Patients cannot be vegetarian.

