14.2 Data to be Analysed

Definition of the analysis populations:

- Full Analysis Set (FAS): All patients enrolled in the study;
- Safety (Safety) population: All patients who are subjected to any invasive procedures and/or take at least one dose of study medication;
- Intention to treat (ITT) population: All patients who take at least one dose of study medication and have evaluable pH monitoring data for at least 1 hour post-dosing;
- Per protocol (PP) population: The criteria for inclusion in the PP population will be confirmed during data checking, but will at least include the following: patients who adhered to the inclusive/exclusive criteria; did not take any prohibited medication which would interfere with evaluation of drugs in the study period; attended visits within the specified visit windows and had complete pH monitoring data for 4 hour post-dosing for both pH monitoring visits.

The ITT population and safety population are the primary populations for evaluation of efficacy and safety, respectively. The PP population will be used for a secondary evaluation of the primary endpoint only.

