6.2. BASELINE

Unless otherwise specified, baseline value refers to the tests or measurements recorded at Visit 1, screening visit. If a particular test or measurement was repeated after Visit 1, screening visit, then the baseline value is defined as the last non-missing measurement taken prior to Visit 2, Day 0 (including unscheduled assessments). In the case where the last non-missing measurement and the reference start date coincide, that measurement will be considered pre-baseline, but Adverse Events (AEs) and medications commencing on the reference start date will be considered post-baseline.

For patients randomized but not treated, baseline is defined as the last non-missing measurement taken on or before the baseline visit date.

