14. STUDY MEDICATION EXPOSURE & COMPLIANCE

At each of the pH monitoring visits, patients will be administered four Compound Sodium Alginate Double Action Chewable Tablets or four matching placebo tablets under the supervision of the Investigator or his or her delegate. No measurement on medication compliance will be performed.

In addition, all patients will then receive Compound Sodium Alginate Double Action Chewable Tablets (two tablets four times daily) as Non-investigational Medicinal Product (NIMP) for symptomatic treatment. The number of tablets dispensed and returned will be recorded in CRF and presented by table and listing.

The following information regarding whether the patients fulfill each requirement prior to pH monitoring and the time interval from each procedure to taking treatment will be summarized by treatment sequence group:

Requirement prior to pH monitoring:

Not taken symptomatic treatment for GERD (antacids etc) in the 24 hours prior to pH monitoring

Abstain from alcohol 24 hours prior to the test meal

Fast for a minimum of 4 hours prior to insertion of manometry probe

Insert manometry probe to aid positioning of esophageal pH sensor prior to consuming test meal

Consume the entire reflux provoking meal

Record pH from 30 minutes prior to dosing to 4 hours post dosing

Time interval from each procedure to taking treatment:

Position pH electrode (90 mins before treatment)

Eat test meal (60 mins before treatment)

Activate pH monitoring data logger and Record (30 mins before treatment)

Stop pH monitoring (4 hour post dose)

The calculation of time interval is provided in section 14.1

Document: Reckitt Benckiser GA1202 Statistical Analysis Plan

Author: [REDACTED]

Version Number:

Final 5.1

Version Date:

[25Feb2014]

Template No: CS_TP_BS016 – Revision 3

Reference: CS_WI_BS005

Effective Date: 01May2012

Page 15 of 29

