16 SAFETY OUTCOMES

All outputs for safety outcomes will be based on the Safety Population.

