16.2 ADVERSE EVENTS

Adverse Events (AEs) will be coded using MedDRA version 16.0. For an individual patient, only adverse events commencing after first dose of IMP and no later than last dose of IMP+1day will be included in the AE and serious adverse event (SAE) summaries. AEs that began prior to the first dose of IMP or more than one day after the final dose of IMP will not be included in the analysis. Where an AE start date is partially or completely missing, and it is unclear using partial dates as to whether the AE is treatment-emergent, it will be assumed that it is.

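### AE percentages are taken over a Safety population that can include undosed patients, although only events after the first IMP dose are counted

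*SAP*

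**What the plan says.** **Who is in the denominator.** SAP 5.2 reads "All patients who are subjected to any invasive procedures and/or take at least one dose of study medication will be included in safety population", which follows protocol 14.2: "All patients who are subjected to any invasive procedures and/or take at least one dose of study medication". Either limb is enough, so a patient can enter without a dose. Protocol 9.6.2, the section on invasive procedures, covers screening blood samples ("Blood samples will be taken for haematology and clinical chemistry at Visit 1 and Visit 3"), endoscopy and pH probe placement. SAP 16 then states: "All outputs for safety outcomes will be based on the Safety Population". SAP 16.2.1 reports numbers and percentages of patients with AEs, by sequence group and in total.

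**What is in the numerator.** For each patient, SAP 16.2 says that "only adverse events commencing after first dose of IMP and no later than last dose of IMP+1day will be included" in the AE and SAE summaries. Protocol 13.1.2 sends untoward events between consent and the first dose to medical history, although SAEs are reportable from consent.

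**Undosed patients are foreseen.** SAP 6.2 has a baseline rule for them: "For patients randomized but not treated, baseline is defined as the last non-missing measurement taken on or before the baseline visit date".

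No sentence in either document restricts the denominator of the AE percentages to dosed patients.

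**The concern.** Numerator and denominator rest on different conditions. To be counted with an AE, a patient must have been dosed. To be counted in the denominator, a patient needs only one invasive procedure. An undosed Safety patient is therefore shown as a patient at risk without an event, although no event in that patient could qualify.

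The error can go in one direction only: it lowers the displayed incidence. Protocol 14.2 makes the Safety population the primary one for the safety evaluation, so these percentages are the ones a reader will take as the AE incidence.

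**Working it through.** The documents give no AE rate, no expected Safety number and no count of undosed patients. There is no stated figure to reproduce, and the inputs marked as assumed below are illustrations.

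**Step 1. Can a randomised patient be in Safety without a dose?** Yes. Inclusion criterion 9 in protocol 10.1 requires "Absence of relevant abnormalities in the physical examination, endoscopy, ECG and laboratory safety results", so blood has been drawn before a patient qualifies. Protocol 9.6.2 treats that draw as an invasive procedure. Every properly randomised patient has thus met the procedure limb before the Visit 2 dose. Protocol 11.3.2.1 describes allocation of the randomisation number, then probe placement, then a meal to be eaten in full, then the dose. SAP 14 places the electrode 90 minutes before treatment. A patient who cannot tolerate the probe or finish the meal could be randomised and not dosed.

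**Step 2. Can that patient contribute an AE?** No. With no first dose, no event can start after it. The missing-data rule in SAP 7.2 does not help, because such a patient has no AE rather than a missing value.

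**Step 3. Size.** Let D be dosed patients, S undosed patients in Safety, and k dosed patients with an AE.

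- Displayed percentage: k/(D+S)
- Percentage among dosed patients: k/D
- Ratio of the first to the second: D/(D+S)

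Inputs: D+S = 44 (planned enrolment, protocol 9.4 and SAP 3.1, taken here as the number randomised); k = 4 (assumed); S = 0 to 3 (assumed).

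| S | D | Displayed k/(D+S) | Among dosed k/D | D/(D+S) |
|---|---|---|---|---|
| 0 | 44 | 4/44 = 9.1% | 4/44 = 9.1% | 1.000 |
| 1 | 43 | 4/44 = 9.1% | 4/43 = 9.3% | 0.977 |
| 2 | 42 | 4/44 = 9.1% | 4/42 = 9.5% | 0.955 |
| 3 | 41 | 4/44 = 9.1% | 4/41 = 9.8% | 0.932 |

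In one sequence column the same formula applies to a smaller base. With an assumed 22 patients in the column, 2 with an AE and one undosed, the display is 2/22 = 9.1% against 2/21 = 9.5% (factor 21/22 = 0.955).

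**Step 4. Does any test change?** McNemar's test depends only on discordant pairs, and an undosed patient could enter only as a pair with no event on either treatment. In an illustrative table with 5 against 2 discordant pairs, the exact p-value is 0.453 whether 0, 8 or 44 such pairs are added. The efficacy analyses use the ITT population, which requires a dose (SAP 5.3), so they are untouched.

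**The case against.** The strongest reply is that there is little room for the effect. The randomisation number goes only to eligible patients at Visit 2, and dosing follows at the same visit under supervision. The window for being randomised and not dosed is short, and protocol section 8 describes an order that would make it shorter still. The baseline rule in SAP 6.2 is a contingency and does not show that such patients are expected. The percentages affected are descriptive, and a sequence column in a crossover is not a treatment contrast. All of this stands, and it is why the point is minor.

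It is also fair that the broad definition is a deliberate choice, identical in protocol and SAP. Endoscopy and probe placement carry discomfort and some risk, so keeping patients exposed to them in the Safety set is defensible. Redefining Safety as dosed patients would remove undosed patients from all Safety-based outputs, including laboratory and vital-sign results. That argues against changing the population. It does not argue against a matching denominator for AE percentages.

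The data review meeting in SAP 5 settles who belongs to each set before database lock, and the classification and pH-procedure listings should make an undosed patient identifiable. Neither gives a denominator rule.

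Two stronger readings are tempting, and the documents support neither:

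- **Screen failures dilute the rates heavily.** SAP 5.2 taken literally would admit a screen failure who had blood drawn. But SAP 9 counts the Safety population by sequence group, and Table 14.1.3 and Listing 16.2.1.3 are based on the FAS, which SAP 5.1 ties to a randomisation number. A screen failure has no sequence. These places suggest that screen failures are not meant to be in Safety, and no screen-failure count is given, so no figure can be attached to that route.
- **The allowance from 44 to 36 means eight undosed patients.** That allowance is for evaluable completers. A patient who leaves after dosing at Visit 2 has been dosed and is correctly in both numerator and denominator.

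**Conclusion.** The mismatch is real and follows from the text as written. Whenever an undosed patient is in the Safety population and at least one dosed patient has a counted AE, the AE percentages in SAP 16.2.1 are too low by the factor D/(D+S).

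The size is likely small and may be zero. Among 44 randomised patients, one to three undosed would mean a relative understatement of about 2% to 7% (1 − 0.977 to 1 − 0.932), or 0.2 to 0.7 percentage points in the example. This rests on the assumed k and S and on Safety being used as a subset of randomised patients. Only descriptive percentages are affected. The point is worth considering because the correction is almost free, not because a safety conclusion is likely to turn on it.

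**What to change.** Keep the Safety population as defined in SAP 5.2 and protocol 14.2. Add one sentence to SAP 16.2: *AE and SAE percentages use as denominator the patients in the Safety population who took at least one dose of IMP.*

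Confirm that the existing SAE listing (16.2.5.3) includes SAEs in patients who had a study procedure but were not dosed. The cut-off in SAP 16.2 is written for summaries and analysis and does not clearly govern listings. No new listing is needed: 16.2.5.3, together with medical history (16.2.3.2) and concomitant illnesses (16.2.3.3), already provides a place for such events.

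The cost is one sentence and one check of listing scope, with no new data. If the sentence is regarded as departing from protocol 14.2, protocol section 14 provides for recording such deviations in the SAP. The only downside is that displayed AE percentages rise slightly if any Safety patient was undosed.
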